11.2 Protocol Deviations

The Principal Investigator is required to follow the protocol. A protocol deviation is an unintended and/or unanticipated departure from the protocol procedures. The Investigator/designee must document and explain in the subject's source documentation any deviation from the approved protocol. Protocol deviations will be documented by the CRA/monitor throughout the course of monitoring visits. Principal Investigator will be notified of deviations in writing by the CRA/monitor. The IRB/IEC should be notified of all protocol violations and deviations according to their IRB/IEC reporting requirements.

11.3 Documentation Required to Initiate Trial

Before the trial may begin, documentation required by US FDA will be provided by the Sponsor. At minimum, documents required to begin a trial in the US include, but are not limited to: a signed protocol acceptance page, and contract; a copy of the official IRB/IEC approval of the trial and the IRB/IEC membership list; current Curricula Vita for the Principal Investigator and any sub-investigator who will be involved in the trial; indication of appropriate accreditation for any laboratories to be used in the trial and a copy of the normal ranges for tests to be performed by that laboratory; completed signed Form FDA 1572 (Statement of Investigator), financial disclosure forms for all investigators listed on Form FDA 1572; site qualification reports, where applicable; verification of Principal Investigator acceptability from local and/or national debarment list(s).

12 DATA HANDLING AND RECORD KEEPING

The PI must maintain a list of appropriately qualified persons to whom he/she has delegated trial duties and should ensure that all persons assisting in the conduct of the trial are informed of their obligations. All persons authorized to make entries and/or corrections on the CRFs are to be included on this document. All entries in the patient's CRF are to be supported by source documentation where appropriate.

Source documents are the original documents, data, records and certified copies of original records of clinical findings, observations and activities from which the patient's CRF data are obtained. These can include, but are not limited to, hospital records, clinical and office charts, laboratory, medico-technical department and pharmacy records, diaries, microfiches, ECG traces, copies or

transcriptions certified after verification as being accurate and complete, photographic negatives, microfilm or magnetic media, X-rays, and correspondence.

The PI and site staff are responsible for maintaining a comprehensive and centralized filing system (Site Trial File/SSF or Investigator Site File (ISF) of all trial-related (essential) documentation, suitable for inspection at any time by representatives from the Sponsor and/or applicable regulatory authorities. The ISF/SSF must consist of those documents that individually or collectively permit evaluation of the conduct of the trial and the quality of the data produced. The ISF/SSF should contain as a minimum all relevant documents and correspondence as outlined in ICH GCP section E6 and 21 CFR Part 312.57, including key documents such as the IB and any amendments, protocol and any amendments, signed ICFs, copies of completed CRFs, IRB/IEC approval documents, Financial Disclosure forms, patient identification lists, enrollment logs, delegation of authority log, staff qualification documents, laboratory normal ranges, records relating to the trial drug including accountability records. Drug accountability records should, at a minimum, contain information regarding receipt, shipment, and disposition.

Each drug accountability record, at a minimum, should contain PI name, date drug shipped/received, date, quantity and batch/code, or lot number for identity of each shipment. In addition, all original source documents supporting entries in the CRF must be maintained and be readily available.

The investigator/institution should maintain the trial documents as specified in Essential Documents for the Conduct of a Clinical Trial and as required by the applicable regulatory requirement(s). The investigator/institution should take measures to prevent accidental or premature destruction of these documents

The Investigator shall maintain adequate records of drug disposition, case histories and any other trial-related records as per 21 CFR Part 312.62 for no less than 2 years after the last marketing application has been approved by FDA; or, in the event that the marketing application has not been approved by FDA, for no less than 2 years after the last shipment / delivery of the drug for investigational use is discontinued and FDA has been notified of the discontinuation.

To enable evaluations and/or audits from regulatory authorities or from the Sponsor or its representative, the investigator additionally agrees to keep records, including the identity of all participating patients (sufficient information to link records e.g., CRFs and medical records), all original, signed informed consent forms, and copies of all CRFs, SAE Reporting forms, source documents, detailed records of treatment disposition, and related essential regulatory documents. The documents listed above must be retained by the investigator for as long as needed to comply with national and international regulations (generally 2 years after discontinuing clinical development or after the last marketing approval). Sponsor will notify the investigator(s)/institutions(s) when the trial-related records are no longer required.

If the investigator relocates, retires, or for any reason withdraws from the trial, both site and sponsor should be prospectively notified. The trial records must be transferred to an acceptable designee, such as another investigator, another institution, or to sponsor. The investigator must obtain the sponsor written permission before disposing of any records, even if retention requirements have

been met. All trial files will be maintained by the Sponsor/Sponsor Representative/CRO throughout the trial, and will be transferred to the Sponsor at the conclusion of the trial.

12.1 Data Collection

Data will be captured via Case Record Form (CRF). All data requested on the CRF must be supported by and be consistent with the patient's source documentation. All missing data must be explained. The Principal Investigator will sign and date each CRF casebook attesting to his/her responsibility for the quality of all data included therein, and that the data represent a complete and accurate record of each subject's participation in the study.

Clinical data management will be performed in accordance with applicable standards. Data cleaning procedures will be performed with the objective of verifying errors and inconsistencies in the data which would otherwise impact on the analysis and reporting objectives, or the credibility of the Clinical Study Report. Adverse events, medical history and concomitant medications will be coded using industry standard dictionaries (MedDRA and WHO Drug).

12.2 Trial Monitoring, Auditing, and Inspecting

The study will be monitored by the Sponsor and/or Sponsor's representatives at all stages of study conduct from inception to completion in accordance with current GCPs. Monitoring will be done in the form of on-site visits, remote monitoring and other communication and will include review of original source documents and CRFs. The frequency of these visits will depend upon the progress of the study, and will include monitoring to assess facilities and equipment, recruiting, record-keeping, protocol adherence, data collection, AE reporting and other factors.

The investigator will permit trial-related monitoring, quality audits, and inspections by the Sponsor or its representatives and government regulatory authorities of all trial-related documents (e.g., source documents, regulatory documents, data collection instruments, case report forms). The investigator will ensure the capability for inspections of applicable trial-related facilities. The investigator will ensure that the trial monitor or any other compliance or QA reviewer is given access to all trial-related documents and trial-related facilities.

Participation as an investigator in this trial implies the acceptance of potential inspection by government regulatory authorities, the sponsor or its representative(s). At the Sponsor's discretion Source Document Verification (SDV) may be performed on all data items or a percentage thereof.

12.3 Medical Monitoring

The sponsor will provide a medical monitor, a medical expert who advises the study investigators and monitors participant safety. The role of the medical monitor is to advise the investigators on study-related medical questions or problems as needed, and to evaluate cumulative participant safety data and make recommendations regarding the safe continuation of the study.

12.4 Quality Assurance and Quality Control

Each trial site shall be required to have Standard Operating Procedures (SOP's) to define and ensure quality assurance/control processes for trial conduct, data generation & collection, recording of data/documentation and reporting according to the protocol, GCP and any applicable local, national or international regulations.

13 DISCLOSURE AND PUBLICATION POLICY

All information provided regarding the trial, as well as all information collected/documentated during the course of the trial, will be regarded as confidential. The Sponsor reserves the right to release literature publications based on the results of the trial. Results from the trial will be published/presented as per the Sponsor's publication strategy.

15 APPENDICES

Appendix A: Contraceptive Guidelines and Pregnancy

Women Not of Childbearing Potential are defined as Follows
Women are considered post-menopausal and not of child bearing potential if they have had 12 months of natural (spontaneous) amenorrhea with an appropriate clinical profile (e.g. age appropriate, history of vasomotor symptoms) or six months of spontaneous amenorrhea with serum FSH levels > 40 mIU/mL] or have had surgical bilateral oophorectomy (with or without hysterectomy) at least six weeks ago. In the case of oophorectomy alone, only when the reproductive status of the woman has been confirmed by follow up hormone level assessment is she considered not of child bearing potential.
Contraceptive Guidelines for Women of Child-Bearing Potential
Women of child-bearing potential, defined as all women physiologically capable of becoming pregnant, must use highly effective contraception during the study and for 5 T1/2 plus an additional 4 weeks after stopping treatment . The highly effective contraception is defined as either:

1. True abstinence: When this is in line with the preferred and usual lifestyle of the subject. Periodic abstinence (e.g., calendar, ovulation, symptothermal, post-ovulation methods) and withdrawal are not acceptable methods of contraception.2. Sterilization: have had surgical bilateral oophorectomy (with or without hysterectomy) or tubal ligation at least six weeks ago. In case of oophorectomy alone, only when the reproductive status of the woman has been confirmed by follow up hormone level assessment.3. Male partner sterilization (with the appropriate post-vasectomy documentation of the absence of sperm in the ejaculate). For female subjects on the study, the vasectomised male partner should be the sole partner for that patient.4. Use of a combination of any two of the following (a+b):
a. Placement of an intrauterine device (IUD) or intrauterine system (IUS).b. Barrier methods of contraception: Condom or Occlusive cap (diaphragm or cervical/vault caps) with spermicidal foam/gel/film/cream/vaginal suppository.

The following are unacceptable forms of contraception for women of childbearing potential:
 
• Oral contraception injected or implanted hormonal methods are not allowed as Tenalisib may potentially decrease the effectiveness of hormonal contraceptives.• IUD progesterone T• Female condom• Natural family planning (rhythm method) or breastfeeding• Fertility awareness• Withdrawal• Cervical shield
Fertile Males

Fertile males, defined as all males physiologically capable of conceiving offspring must use condom during treatment, plus additional 12 weeks after stopping treatment and should not father a child in this period.

Pregnancies

To ensure patient safety, each pregnancy in a patient on study treatment must be reported to Rhizen Pharmaceuticals SA within 24 hours of learning of its occurrence. The pregnancy should be followed up for 3 months after the termination of the pregnancy to determine outcome, including spontaneous or voluntary termination, details of the birth, and the presence or absence of any birth defects, congenital abnormalities, or maternal and/or newborn complications. Consent to report information regarding these pregnancy outcomes should be obtained from the mother.

Pregnancy is not considered a SAE. Initial and follow up information should be recorded on a Clinical Study Pregnancy Form and reported by the investigator to Rhizen Pharmaceuticals SA. Pregnancy follow-up should be recorded on the same form and should include an assessment of the possible relationship to the investigational drugs to any pregnancy outcome will also be captured on the pregnancy form. Any SAE experienced during pregnancy must be reported on the SAE Report Form.

Pregnancy outcomes must be collected for the female partners of any males who took study treatment in this study. Consent to report information regarding these pregnancy outcomes should be obtained from the mother.

STATISTICAL ANALYSIS PLAN

PROTOCOL NO. RP6530-1803

**An Open label, Compassionate Use Study of Tenalisib
(RP6530) in Patients currently receiving treatment on Tenalisib
trials in Hematological Malignancies**

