4 SELECTION AND WITHDRAWAL OF SUBJECTS

4.1 Inclusion Criteria

Patients must meet all inclusion criteria to be eligible for participation in this study:

1. Patients must be currently receiving treatment with Tenalisib either as monotherapy or in combination with another agent on a previously approved protocol for hematological malignancies including but not limited to indications DLBCL, iNHL, PTCL, CTCL, CLL and HL.
2. Patients must have had at least one efficacy evaluation following the initiation of Tenalisib in previous study and should have achieved either SD, PR or CR.
3. Patients must have completed at least 6 cycles of Tenalisib in previous study
4. Ability to swallow and retain oral medication.
5. Female patients of child-bearing potential must consent to use two medically acceptable methods of contraception throughout the study period and for 4 weeks after the last dose of Tenalisib. A barrier method of contraception must be included.
6. Male patients must be willing to use adequate contraceptive measures throughout the study period and for 12 weeks after the last dose of Tenalisib.
7. Willingness and ability to comply with trial and follow-up procedures.
8. Willingness to provide new written informed consent.

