7.4.1 Pregnancy, Abortion, Birth Defects/Congenital Anomalies

Female patients of child-bearing potential (see Appendix A) must consent to use two medically acceptable method of contraception throughout the study period and for 4 weeks after the last dose of Tenalisib.

During the course of the trial, all female patients of childbearing potential and pregnant partner of male subjects must contact the treating investigator immediately if they suspect that they may be pregnant (a missed or late menstrual period should be reported to the treating investigator).

If an investigator suspects that a patient may be pregnant after the patient has been receiving trial drug(s), the trial drug(s) must immediately be withheld until the result of the pregnancy test is confirmed. If a pregnancy is confirmed, the trial drug(s) must be immediately and permanently stopped, the patient must be discontinued from the trial, and the investigator must notify the medical monitor and Sponsor Representative as soon as possible. If a patient becomes pregnant while enrolled in the trial, a Pregnancy Form should be completed and mailed to the Sponsor. The outcome of the pregnancy will be monitored as outlined in Appendix A.

Congenital anomalies/birth defects always meet SAE criteria, and should therefore be expeditiously reported as an SAE, using the previously described process for SAE reporting. A Pregnancy Form should also have been previously completed and will need to be updated to reflect the outcome of the pregnancy.

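### The contraception rules for women of child-bearing potential conflict between inclusion criterion 5, section 7.4.1 and Appendix A, mainly on accepted methods and to a lesser degree on duration

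*Combined protocol and SAP*

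**What the plan says.** Three parts of the protocol set contraception rules for women of child-bearing potential.

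- **Inclusion criterion 5** (synopsis and section 4.1, same wording) requires "two medically acceptable methods of contraception throughout the study period and for 4 weeks after the last dose of Tenalisib". It adds: "A barrier method of contraception must be included". It does not refer to Appendix A.
- **Section 7.4.1** repeats the two methods and the same period, "throughout the study period and for 4 weeks after the last dose of Tenalisib". It leaves out the barrier sentence. It opens "Female patients of child-bearing potential (see Appendix A) must consent", so its pointer to the appendix is attached to the term child-bearing potential.
- **Appendix A** sets the post-treatment period as "for 5 T1/2 plus an additional 4 weeks after stopping treatment". It introduces its methods with "The highly effective contraception is defined as either" and lists four alternatives: true abstinence; sterilisation (bilateral oophorectomy or tubal ligation); a sterilised male partner who is the sole partner; or an intrauterine device or system combined with a barrier. A separate list of unacceptable methods rules out oral, injected and implanted hormonal contraception, on the ground that Tenalisib may make it less effective.

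Section 3.4.5 explains why post-treatment contraception is advised at all: there are no reproductive toxicity or genotoxicity data.

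**The concern.** Criterion 5 is an eligibility condition, and section 4.1 requires every inclusion criterion to be met. If the eligibility list and the appendix accept different methods, whether a given woman is eligible depends on which page the site uses. Enrolling her can be correct under one and a deviation under the other.

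The rules also protect patients, and few other safeguards stand behind them. The protocol requires no pregnancy tests (section 6.3 and the Table 1 note leave them to standard of care), visits are 3 months apart, and a 3-month drug supply is dispensed at each visit. The contraception instructions therefore carry much of the protection against exposure in pregnancy.

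**Working it through.** No sample size, power or event count enters this point, and the plan gives no figure to reproduce. The check is a comparison of texts plus one subtraction.

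**Step 1: the rules side by side**

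| Feature | Criterion 5 | Section 7.4.1 | Appendix A |
|---|---|---|---|
| Number of methods | Two | Two | Any one of four options |
| Barrier required | Yes | Not stated | Only within option 4 |
| Hormonal methods | Not mentioned | Not mentioned | Oral, injected and implanted barred |
| Time after last dose | 4 weeks | 4 weeks | 5 half-lives + 4 weeks |

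**Step 2: each Appendix A option tested against criterion 5**

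| Appendix A option | Two methods? | Barrier? | Meets criterion 5 as worded? |
|---|---|---|---|
| 1. True abstinence | No | No | No |
| 2. Tubal ligation | No | No | No |
| 2. Bilateral oophorectomy | – | – | Not a clean test (step 3) |
| 3. Vasectomised sole partner | No | No | No |
| 4. Intrauterine device or system plus barrier | Yes | Yes | Yes |

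**Step 3: does the definition of child-bearing potential remove the conflict?** Appendix A treats a woman as not of child-bearing potential if she is post-menopausal or has had bilateral oophorectomy, with hormone confirmation where oophorectomy was the only surgery. Such women fall outside criterion 5, so oophorectomy is not an example of the conflict. Tubal ligation, abstinence and a sterilised partner are not in that definition. Appendix A lists them as methods for women who are of child-bearing potential, so criterion 5 still applies to them.

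**Step 4: the opposite direction.** A hormonal method plus a condom is two methods with a barrier. Neither criterion 5 nor section 7.4.1 excludes hormonal methods or says what counts as medically acceptable, so the pair can be read as meeting both. Appendix A does not allow it.

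**Step 5: duration.** With T the half-life in days:

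- Criterion 5 and section 7.4.1: 4 × 7 = 28 days.
- Appendix A: 28 + 5T days.
- Gap: (28 + 5T) − 28 = 5T, which is above zero for any half-life.

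The documents do not give T. Over an assumed range of 2 to 24 hours:

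- T = 2 h: 5 × 2 = 10 h, or 10/24 ≈ 0.4 days; Appendix A total ≈ 28.4 days.
- T = 24 h: 5 × 24 = 120 h, or 5 days; Appendix A total = 33 days.

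Because the half-life is not stated, a site cannot turn the Appendix A period into a calendar date from the protocol alone.

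**The case against.** The strongest reply is that this is an editing inconsistency that a careful site can work around. The rules are not mutually exclusive: Appendix A's option 4, kept up for the longer period, satisfies every section at once. Appendix A presents itself as guidance and could be read as spelling out what criterion 5 leaves undefined. The half-life may be in the Investigator's Brochure, to which the protocol refers for product information. The patients have already completed at least 6 cycles under an earlier protocol. The documents do not say how many of the approximately 50 are women of child-bearing potential. No endpoint or analysis is touched.

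Much of this stands. The practical reach is unknown, and the duration gap may be trivial. But reading Appendix A as detail for criterion 5 cannot make options 1 and 3, or tubal ligation under option 2, into two methods with a barrier. Nor does anything in criterion 5 carry over the exclusion of hormonal methods.

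A reader might also infer three stronger things that the documents do not support:

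- **That section 7.4.1 adopts both rules at once.** It does not. Its opening reference to Appendix A qualifies the term child-bearing potential, and its other reference concerns follow-up of pregnancy outcome. On methods and duration it states only the two-method, 4-week rule.
- **That every form of sterilisation in Appendix A conflicts with criterion 5.** Bilateral oophorectomy also appears in the definition of women not of child-bearing potential; tubal ligation does not.
- **That following criterion 5 leaves women materially unprotected after treatment.** They would stop earlier than Appendix A says, but by an amount that cannot be sized from the documents.

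**Conclusion.** The contradiction is in the current text, and no section resolves it. The conflict over methods is the weightier part and rests on no assumption. It runs both ways: true abstinence, tubal ligation and a vasectomised sole partner satisfy Appendix A and fail criterion 5 as worded, while a hormonal method plus a condom can pass criterion 5 and is barred by Appendix A. The second case matters because the appendix itself says the drug may weaken hormonal contraception, and a site working only from the eligibility list would not see that.

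The duration conflict is real but secondary. It equals 5 half-lives; the figure of about 0.4 to 5 days depends wholly on the assumed half-life of 2 to 24 hours.

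This is an internal inconsistency bearing on eligibility and patient safety. It does not affect the endpoints or the statistical analysis. No view is taken on which rule is right.

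**What to change.** Reconcile the synopsis, section 4.1 criterion 5, section 7.4.1 and Appendix A so that all carry the same rule:

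- one post-treatment duration, stated in days or weeks, so that a site can calculate the end date without needing a half-life;
- one list of accepted methods and one of excluded methods, including a clear statement on how many methods are needed, whether a barrier is mandatory, and the status of hormonal methods;
- an explicit reference to that list from criterion 5 and section 7.4.1, attached to the methods and the duration as well as to the definition of child-bearing potential.

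The sponsor decides the content of the rule. The cost is amendment wording, plus consent wording if the consent form repeats any of the affected text; the consent pages were not available to check. No data collection or analysis changes.
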